- a) Obesity is a well-known epidemic in the US with prevalence nearing 40%. [1] Obesity is a risk factor for a myriad of disease states including osteoarthritis (OA) due to increased load on the weightbearing joints. Therefore, patients with obesity, and namely those with body mass index (BMI) approaching $>40\text{kg}/\text{m}^2$ (class III obesity), suffer from OA disproportionately compared to their non-obese peers. [2] As this population frequently reports to arthroplasty clinics, studies have identified increased rates of post-operative complications following total joint arthroplasty (TJA) specifically in the class III obese population. [2-5] To combat this increased risk, arthroplasty surgeons traditionally have excluded this population from their surgical practice or encouraged their patients to lose weight in order for their BMI to drop below $40\text{kg}/\text{m}^2$; however, these practices have been recently questioned. [6-8]

With the validity of lowering BMI to improve TJA outcomes being questioned, studies have made efforts to identify more patient-specific factors such as body composition. Body composition can be identified through several modalities including anthropomorphic measurements, DEXA, MRI, and CT. [9-11] In addition, bioimpedance

analysis (BIA) offers rapid, accurate, and non-invasive assessment without the use of ionizing radiation. [9, 12, 13] BIA can be completed through multiple devices including a stationary, scale-like device, a portable ECG-like device, or even wearable wristbands.

Our group has conducted numerous studies focusing on body composition in arthroplasty patients, including changes they experience following surgery and pre-operative risk identification. By employing both clinic-based and home-based assessments more frequently than patients would normally have, this study aims to identify any benefit, if any, a wearable BIA device serves in an obese-arthroplasty population.

3) Study Aims

- a) Aims:
 - i) To identify if the use of a wearable BIA wristband aids in the desired body composition changes (body mass loss, fat mass loss, skeletal muscle mass gain)
 - ii) To quantify the body composition changes exhibited by each cohort
 - iii) To track surgical outcomes for those patients that are indicated for total joint arthroplasty
- b) Hypotheses:
 - i) The wearable group will exhibit the desired body composition changes more rapidly than the control group

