 - ii) The wearable group will exhibit greater desired body composition changes more rapidly than the control group
 - iii) The wearable group will less post-operative complications than the control group

4) Administrative Organization

- a) This study will solely be completed at the University of Iowa Healthcare and Clinics Department of Orthopaedics and Rehabilitation.

5) Study Design

- a) Experimental design of the study: randomized controlled trial with single blinding
- b) Study population general description
 - i) Specify total number of adult subjects, age range and percent by gender
 - (1) 90 subjects (>18 years old)
 - (2) 50% male, 50% female
 - ii) Specify total number of minor subjects (less than 18 years of age), age range and percent by gender.
 - (1) none
- c) Sample size determination and power analyses
 - i) A power analysis was performed by the orthopedic department statistician [name].
- d) Study outcomes/endpoints
 - i) Primary outcomes
 - (1) Muscle mass, body mass, and fat mass changes from baseline at 3-, 6-, 9-, and 12-months
 - ii) Secondary outcomes
 - (1) Time to achieve desired body composition changes
 - (2) Time to TJA indication
 - (3) Surgical outcomes for those that undergo TJA

6) Study Procedures

- a) Describe Subject selection procedures
 - i) Describe the sampling plan including Inclusion/Exclusion criteria (subject and disease characteristics)
 - (1) Inclusion Criteria
 - (a) Adults > 18 years
 - (b) BMI > 40kg/m2
 - (c) Presenting to arthroplasty-obesity clinic with desire for total joint arthroplasty procedure
 - (d) Owns a smartphone capable of handling iOS or Google Play apps
 - (2) Exclusion Criteria
 - (a) Has a pacemaker or other electronic pacemaker placement
 - (b) Inability to complete study protocols
 - (c) Inability to stand unsupported for 60-90 seconds
 - ii) Indicate if the study plans to enroll non-English speaking subjects. If so, specify language(s), who will translate documents, who will serve as a translator. The IRB must review and approve all translated documents.
 - (1) This group will not be enrolled
 - iii) Indicate if the study will enroll subordinates of the PI or a member of the research team.
 - (1) This group will not be enrolled
 - iv) Indicate if the study will enroll pregnant women for research on fetuses and neonates
 - (1) This group will not be enrolled

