- c) Confidentiality / Data Security Plans – Refer to the Data Security Educational Tool and the Protecting Sensitive Data page of the UI ITS website. Specify plans for transmitting, transporting and/or storing:
 - i) Paper records
 - (1) Informed consent documents to be kept in PI's locked office
 - ii) Electronic records - Specify who is responsible for maintaining security. Researchers are advised to consult with the departmental IT representative to establish a data security plan that is appropriate to the level of security of the data being collected/stored for the project.
 - (1) Standard protections on departmental server
 - iii) Biospecimens - Specify who is responsible for maintaining security.
 - (1) N/A
- d) Plans for sharing data or taking data outside the UI
 - i) N/A

8) Risks and Benefits

- a) Describe all possible risks (physical, emotional or psychological, financial, legal or social risks).
 - i) Risks include loss of information/privacy, falling off stationary BIA scanner, hand pain from hand grip strength testing.
- b) Describe all steps to minimize any possible risk to subjects.
 - i) Data will only be accessed by need-to-know study members, a study team member will supervise and “spot” the subject on the stationary BIA scanner, patient will be advised to take rests in between hand grip strength testing to minimize pain.
- c) Describe all guaranteed direct benefits to subjects (do not include compensation or hypothesized results).
 - i) None
- d) Describe potential benefits to society from the results of the research.
 - i) Future patients will benefit from knowing if wearable technology has an effect or not.

9) Safety Monitoring Plan

- a) N/A

10) Data Analysis Plan

- a) Describe statistical analysis methods as appropriate. Consult with a biostatistician, if appropriate. The analysis plan should correspond with the data collection described in the Study Procedures section. Describe plans for intent-to-treat methodology and any sample stratification.
 - i) Noninferiority comparison of the primary outcome and secondary outcome between the treatment groups at each time points.
 - ii) Multivariate analysis to compare patient demographics between the two treatment arms.
 - iii) Non-parametric tests such as ANOVA and ANCOVA will be utilized to determine if there is any difference between the two groups.
- b) Provide the rationale or power analysis to support the number of subjects proposed to complete the study.

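### Section 10(a)(i) plans a noninferiority comparison with no margin, while Aim i, the hypotheses and the power statement concern a difference, and no item is named as deciding success

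*Combined protocol and SAP*

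**What the plan says.** Section 10(a) has three items.

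- Item i) is a "Noninferiority comparison of the primary outcome and secondary outcome between the treatment groups at each time points". It gives no margin, no direction and no alpha or interval rule, and no margin appears elsewhere.
- Item ii) compares demographics only.
- Item iii) states: "Non-parametric tests such as ANOVA and ANCOVA will be utilized to determine if there is any difference between the two groups". It names no outcome and no time point.

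The rest of the protocol is worded as a search for benefit.

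- Aim i in section 3(a) is "To identify if the use of a wearable BIA wristband aids in the desired body composition changes", and it lists loss of body mass, loss of fat mass and gain in skeletal muscle.
- The hypotheses in section 3(b) are "The wearable group will exhibit the desired body composition changes more rapidly than the control group", "The wearable group will exhibit greater desired body composition changes more rapidly than the control group" and "The wearable group will less post-operative complications than the control group".
- Section 8(d)(i) gives the value to society as learning whether wearables have an effect.
- Section 10(b) sizes the trial to detect a difference of 1.676.

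The primary outcomes in section 5(d)(i) are "Muscle mass, body mass, and fat mass changes from baseline at 3-, 6-, 9-, and 12-months", that is, three measures at four visits.

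**The concern.** Both arms receive the same coaching, and the wristband is added in one arm. Showing that coaching plus wristband is not worse than coaching alone does not by itself show that the wristband helps, which is what Aim i asks. A noninferiority comparison without a margin also has no defined hypothesis: whether it succeeds depends on a number that could be chosen after the data are seen.

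Two items could each be read as the main analysis, and the plan ranks neither. Suppose the result were noninferior at some margin, with no difference found. That would be a legitimate finding, but the plan does not say whether the trial had then met its aim.

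There is also a mismatch in time basis. Item i) compares the arms visit by visit, whereas the power statement rests on repeated measurements taken together.

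**Working it through.** **Inputs, all from section 10(b):** 44 per arm; difference 1.676; SD 3.610; five measurements; compound symmetry with correlation 0.500; alpha 0.050; power 80%. Sidedness, measure and unit are not stated. The calculations use the normal approximation and complete data.

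**1. Reproduce the plan's figure.** SD of a patient's five-measurement average:

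3.610 × √[(1 + 4 × 0.5)/5] = 3.610 × √0.600 = 2.796.

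Patients per arm, two-sided 0.05, 80% power:

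2 × (1.960 + 0.842)² × 2.796² / 1.676² = 43.7, rounded up to 44.

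At 44 per arm, SE = 2.796 × √(2/44) = 0.596 and 1.676/0.596 = 2.81, so power = Φ(2.81 − 1.96) = 80.3%. A one-sided 0.05 test would need 34.4 per arm, which does not match. The stated size is therefore that of a two-sided difference test on the five-measurement average.

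**2. What the missing margin does.** The documents give no margin, so the margins here are assumptions: 0.5, 1 and 1.5 times 1.676. With true difference 0 and one-sided 0.025, power = Φ(margin/SE − 1.96). At a single visit, SE = 3.610 × √(2/44) = 0.770.

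| Assumed margin | Five-measurement average, 44 per arm | Single visit, 44 per arm |
|---|---|---|
| 0.838 | 29% | 19% |
| 1.676 | 80% | 59% |
| 2.514 | 99% | 90% |

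**3. A difference test at one visit.** This is the time basis of item i). Power = Φ(1.676/0.770 − 1.96) = about 59%. At correlation 0.5 the figure is the same for an unadjusted visit value and for a change from baseline, because 3.610 × √[2 × (1 − 0.5)] = 3.610. If 3.610 and 0.500 describe visit values, baseline adjustment lowers the SD to 3.610 × √(1 − 0.5²) = 3.126 and raises power to about 71%, still below 80%.

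**4. Power of a difference test over the four follow-up visits, 44 per arm.**

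- If 3.610 and 0.500 describe values at each visit, with baseline as covariate: variance factor (1 + 3 × 0.5)/4 − 0.5² = 0.375; SD 3.610 × √0.375 = 2.211; SE 0.471; power about 94%.
- If they describe changes from baseline: variance factor (1 + 3 × 0.5)/4 = 0.625; SD 2.854; SE 0.608; power about 79%. Any gain from baseline adjustment would come on top, but the documents do not allow it to be computed.

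**5. If all three measures stay primary and any one may decide success.** Bonferroni gives alpha 0.05/3 = 0.0167 and a critical value of 2.394. Power per measure on the five-measurement average is Φ(2.81 − 2.394) = about 66%, assuming the same standardised effect for each measure.

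**The case against.** The strongest reply is that one word in one line is a slip. Item 10(a)(iii) plans a test for a difference, and the aim, hypotheses, section 8(d)(i) and power statement all point the same way. Much of this stands. A reader might infer that the plan contains no difference test, so that Aim i would go unanswered. The documents do not support that, because item iii) may well be meant as the method for item i). What remains is that item iii) names no outcome or time point, and nothing says that it governs. If the word is a slip, correcting it costs nothing.

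A second reply is that a not-worse question has some meaning here, since section 6(g) lets patients keep or reduce body mass. That is fair for body mass. It does not carry over to fat and muscle, where the clinic goals have a direction, and Aim i itself lists body mass loss. It is also true that the confidence interval from a noninferiority analysis could show benefit if it excluded zero, but the plan states no such step.

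A third reply is that 44 per arm also fits a noninferiority margin of 1.676 at one-sided 0.025 with no true difference. The arithmetic agrees. The text, however, presents 1.676 as a difference to detect, gives alpha as 0.050 and names no margin.

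**Conclusion.** The point holds. The only item that names the primary and secondary outcomes specifies a comparison that cannot be judged without a margin and that does not match the trial's question. A second, difference-based item leaves its outcome and time point open, and the plan does not say which of the two decides success.

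The size of the problem is the dependence on an unstated margin: 29% to 99% power on the five-measurement average, and 19% to 90% at a single visit, over the assumed margins. These figures assume a true difference of 0, one-sided 0.025, complete data and the plan's own SD and correlation. Separately, the visit-by-visit basis gives about 59% power for an unadjusted difference of 1.676, not 80%.

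A reader might also infer that the sample size is wrong. It is not: 44 per arm is correct for a two-sided difference test on the five-measurement average. Nor do the 94% and 79% figures measure the defect. They show what a corrected analysis could achieve, and the 94% holds only if 3.610 and 0.500 describe values at each visit.

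**What to change.** - In 10(a)(i), replace the noninferiority comparison with a two-sided alpha 0.05 superiority (difference) comparison of wearable versus control. Remove the noninferiority wording for the secondary outcomes as well.
- State that 10(a)(iii) is the method for this comparison. Use the ANCOVA it already names, with the baseline value as covariate, and drop the non-parametric label, which does not fit ANOVA or ANCOVA.
- Make the deciding test the group effect over the 3-, 6-, 9- and 12-month visits, in line with the repeated-measures basis of the power statement, and treat single-visit comparisons as supportive. Baseline is a covariate and is not counted in the averaged effect, since it precedes randomisation and cannot carry a treatment effect.
- State which of the three primary measures 1.676 and 3.610 refer to, and whether they describe values at each visit or changes from baseline.
- The three primary measures need not be cut to one. If all stay primary and any one can decide success, state the multiplicity rule and restate the power.

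The cost is wording edits only, with no added patients, visits or data. The stated power may become less favourable: about 79% before any gain from adjustment if the inputs are changes from baseline, or about 66% per measure under Bonferroni over three on the five-measurement average. Dropout or early exit to surgery would lower these figures further.

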 - (a) Patients will be provided a BIA wearable (InBody BAND 2) and instructions regarding downloading smartphone app. Education regarding the device and app will be provided. In addition, they will receive the standard procedures/education provided in arthroplasty-obesity clinic
 - (2) Control group
 - (a) They will receive the standard procedures /education provided in arthroplasty-obesity clinic
- g) Describe all study assessments and activities
 - i) Provide a thorough, detailed description
 - (1) Randomization
 - (a) Once enrolled, patients will be randomized by a non-PI study member. Randomization will occur after the clinic standard education as to not be influenced based on randomization group.
 - (2) All patients
 - (a) All patients will experience a “coaching” period and be eligible for a “surgical period”. All patients (study and control) will undergo the clinic standard operating procedures of stationary BIA, hand-grip strength, and exercise and nutritional education (weight/resistance training, low carbohydrate/high protein diet) in the “coaching” period. All patients will also be advised of the goal to maintain or lose body mass, lose body fat, and gain muscle mass, which is also clinic standard operating procedure. Patients will follow-up in the clinic per standard protocol at approximately every 3 months (± 1 month). At each visit, stationary BIA, hand-grip strength, and exercise and nutritional coaching will be repeated, as is standard in clinic. All patients will be eligible to be indicated for TJA at the PI’s discretion. Per clinic procedures, patients are indicated for TJA as they achieve their body composition goals (maintain or lose body mass, lose body fat, and gain muscle mass). All patients will be instructed to not discuss their study arm (wearable or control) with the PI. Patients are eligible to enter the surgical period at any point during the coaching period. If patients feel that they meet their goals prior to they are eligible to reschedule their appointment sooner than the next visit. All patients will receive a phone call from a study team member every 1 month to assess compliance with study arm and check in on perceived progress.
 - (3) Wearable group

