 - (a) If patients are randomized the wearable group, they will be provided a wearable and instructions on installing the app and its features. They will be instructed to take BIA measurements at least weekly via the wearable. The wearable group will be instructed at the beginning of each visit to remove and keep their wearable out of sight of the PI during their visit.
 - (4) Patients who enter “Surgical” period

- (a) Patients who are indicated for TJA (at the PI's discretion) will leave the coaching period and enter the surgical period. Patients' medical record will be followed if they are indicated for TJA for post-operative outcomes such as infection, reoperation, implant failure. Surgical follow-up will occur for up to 24 months following study enrollment.
- ii) Provide a schedule of all study assessments and subject activities, including a tabular representation or timeline as applicable
 - (1) See **Table I** below
- h) Recontacting Subjects Lost to Follow Up – Indicate if the researcher will attempt to locate subjects if the research team is unable to reach them through the contact information they provided. Describe the procedures and justification for these efforts to locate subjects.
 - i) Research members will not contact the patients lost to follow, as standard clinic procedures have nursing staff contact the patients.
- i) Subject Compensation
 - i) Specify compensation method(s)
 - (1) Patients will not be compensated monetarily. Those randomized to the study cohort will be able to keep their wearable device, if desired.
 - ii) Describe the compensation plan, including amount per visit, total compensation amount, pro-rating for early withdrawal
 - (1) N/A
 - iii) Indicate whether the study will use the departmental cash handling plan or obtain approval from Accounting Services for a study-specific cash handling plan.
 - (1) N/A

7) Privacy and Confidentiality Protections

- a) Describe privacy protections – collecting data in a private space, collecting the amount and type of information you need to answer your research question(s)
 - i) Only the minimum necessary data will be collected. The data collected will be done in a private clinic room.
- b) Describe plans and justification for collecting social security number (SSN)
 - i) N/A

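### The two secondary time outcomes have no censoring-aware analysis; one log-rank superiority comparison each, with sensitivity analyses for dropout, would fit the hypotheses better

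*Combined protocol and SAP*

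**What the plan says.** Section 5(d)(ii) lists as secondary outcomes "Time to achieve desired body composition changes" and "Time to TJA indication". The first hypothesis in section 3(b) is "The wearable group will exhibit the desired body composition changes more rapidly than the control group", which is a superiority claim about speed; the second hypothesis also refers to speed.

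Section 10(a) gives the analysis. Item (i) is "Noninferiority comparison of the primary outcome and secondary outcome between the treatment groups at each time points", and no margin is stated. Item (iii) is "Non-parametric tests such as ANOVA and ANCOVA will be utilized to determine if there is any difference between the two groups". Item (ii) concerns demographics only. No Kaplan–Meier, log-rank, Cox or interval-censored method appears in the document, and there is no censoring rule or time origin.

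Section 6(g)(i) describes how events come to be observed. Clinic visits are about three months apart, with a one-month allowance either way. For patients who think they have met their goals, "they are eligible to reschedule their appointment sooner than the next visit". Of the wearable arm only, the protocol says: "They will be instructed to take BIA measurements at least weekly via the wearable". TJA indication is at the principal investigator's discretion and ends the coaching period. Under section 6(h) the research team does not recontact patients who are lost.

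The goal is described in two ways. The aims in section 3(a)(i) require body mass to fall; section 6(g)(i)(2) also accepts stable body mass.

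**The concern.** A time-to-event variable has one value per patient, so comparing it visit by visit is not a usable instruction. Nothing guarantees that every patient reaches the goal or is indicated by month 12, and some will leave earlier. ANOVA and ANCOVA need a number for each of these patients, and the plan supplies none. The analyst would have to choose after seeing the data, and the choices differ in power and in error rate. A noninferiority comparison without a margin also cannot test a hypothesis of faster change. At stake is whether the outcomes that bear most directly on the speed hypotheses are analysed in a way that can answer them.

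**Working it through.** **The plan's own power figure.** Section 10(b) gives 44 per arm, difference 1.676, SD 3.610, correlation 0.500, 5 measurements and alpha 0.050. The effective SD of a patient's mean is 3.610 × √[(1 + 4 × 0.5)/5] = 2.796. Then n = 2 × (1.960 + 0.842)² × 2.796² / 1.676² ≈ 43.7, so 44 per arm (two-sided). The figure reproduces, but it concerns a repeated continuous measure and says nothing about the time outcomes.

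**Assumptions for the time outcomes.** The documents give no event or dropout rates. Assume 44 per arm, visits at months 3, 6, 9 and 12, and goal rates per visit of 15% (control) against 25% or 30% (wearable). The probability of the event by month 12 is:
- control: 1 − 0.85⁴ = 0.478
- wearable: 1 − 0.75⁴ = 0.684, or 1 − 0.70⁴ = 0.760

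**Hand check of log-rank power.** The hazard ratio is ln 0.75 / ln 0.85 = 1.77, or ln 0.70 / ln 0.85 = 2.19. Expected events are 44 × (0.478 + 0.684) = 51.1, or 44 × (0.478 + 0.760) = 54.5. By Schoenfeld's formula, power = Φ(√(events/4) × ln HR − 1.96):
- 15% vs 25%: Φ(3.575 × 0.571 − 1.96) = Φ(0.08) = 53%
- 15% vs 30%: Φ(3.690 × 0.786 − 1.96) = Φ(0.94) = 83%

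**Simulated power**, two-sided 0.05, 6,000 trials per scenario (5,000 for the Bonferroni row). Dropout is 10% per visit (1 − 0.9⁴ = 34% by month 12), unrelated to outcome. Each cell gives 15% vs 25% / 15% vs 30%.

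| Analysis | No dropout | 10% dropout per visit |
|---|---|---|
| Log-rank | 52% / 82% | 44% / 73% |
| ANOVA, achievers only | 8% / 12% | 7% / 10% |
| Non-achievers kept at a final time or last rank | 42–49% / 72–80% | 33–38% / 59–64% |
| Month-12 status alone | 49% / 79% | 39% / 66% |
| Status at four visits, Bonferroni | 42% / 72% | 32% / 59% |

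A second model gives the same order. It uses exponential times, hazard ratio 2.0, 10% dropout over 12 months, and 30/50/70% of controls with the event by month 12. Power is 6/12/26% for achievers only, 37/60/74% with censored times treated as event times, and 52/71/81% for log-rank. With no effect, all three reject about 5% of the time.

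**When dropout differs by arm.** No true effect, 5% vs 15% dropout per visit:

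| Who leaves | Log-rank error | Non-achievers kept |
|---|---|---|
| Unrelated to outcome | 4.7–4.8% | 7.6–14.1% |
| Non-achievers at four times the achievers' rate | 6.7–8.0% | 5.5–5.7% |
| Only patients who would not achieve by month 12 | 8.1–9.6% | 4.9–5.4% |

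The last two rows used 4,000 trials and ranked non-achievers last. With equal 10% dropout, power for log-rank against last rank is 48%/78% vs 50%/80% if only non-achievers leave, and 45%/76% vs 45%/75% if they leave at four times the rate.

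**Early visits.** No true effect; half of wearable achievers and no controls come in early; 30/50/70% achieve by month 12. Log-rank error on actual dates is 5.2/5.7/6.6%. In the all-versus-none extreme it is 5.4/6.8/10.0%. Dating the goal by scheduled visit in both arms gives 4.9–5.4%. If 10–20% of goals are lost again before the scheduled visit (50–70% achieving, half early), error is 6.4–13.2% on actual dates and 5.2–8.7% with visit dating.

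**The case against.** The best defence is that the plan is underspecified rather than committed to a wrong test. ANOVA and ANCOVA are offered as examples, and the log-rank test is itself non-parametric, so it is not excluded. This stands, but no censoring-aware method is named anywhere, and the choice is left until data are in hand.

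A reader might infer that the trial will lose most of its power on these outcomes, from 52% to 8%. The documents do not support that: nowhere do they say that non-achievers are dropped. The most literal reading of a comparison at each time point is goal status by visit. Without dropout, month-12 status is only about 3 points below log-rank.

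A reader might also infer that a log-rank test cures the problem. It does so only if dropout is unrelated to outcome. Patients making no progress may be the ones who stop attending; the documents give no data either way. In that case the error-rate ranking reverses.

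Nor should one conclude that the plan carries a known multiplicity error. Four unadjusted superiority tests of status would give a 12.7–14.5% chance of at least one p < 0.05 per outcome. But item (i) specifies noninferiority, and without a margin its error rate cannot be computed.

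Finally, these are secondary outcomes for which the trial was not sized. That limits the severity but does not remove the mismatch with the hypotheses.

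**Conclusion.** The concern holds in a limited form. The specified comparison cannot be carried out sensibly on a time outcome, runs against the direction of the hypotheses, and leaves patients without the event undefined. One log-rank comparison per outcome is better matched to the question.

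Under the assumed rates, its gain over keeping non-achievers at a final time or rank is about 2 to 10 points without dropout (52% vs 42–49%; 82% vs 72–80%). With 10% dropout per visit unrelated to outcome, the gain is about 6 to 14 points (44% vs 33–38%; 73% vs 59–64%). The gain disappears if mainly non-achievers leave, and log-rank error can then reach about 8–10% when dropout also differs by arm. Distortion from early visits is small for the log-rank test in most scenarios, though larger if goals are often lost again. All rates are assumptions. This should be changed before analysis, but it does not threaten the primary outcomes.

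**What to change.** - **10(a)(i):** exclude the two time outcomes from the noninferiority, visit-by-visit comparison. State one two-sided superiority comparison per outcome in all randomised patients: Kaplan–Meier curves and a log-rank test from randomisation. Censor patients without the event at their last clinic assessment, no later than the month-12 visit.
- **Dropout:** add a sensitivity analysis that keeps patients who leave without the event as non-achievers to month 12.
- **TJA indication before the goal:** indication ends coaching, so for the body-composition outcome report how many patients were indicated before the goal was recorded, with a sensitivity analysis for them.
- **Goal definition:** before analysis, reconcile sections 3(a)(i) and 6(g)(i)(2) into one event definition based on the clinic's stationary bioimpedance measurement. Which definition is right is for the investigators to settle.
- **Early visits:** report unscheduled visits by arm. Add a sensitivity analysis that dates the body-composition goal at the next scheduled visit in both arms. No detailed visit-window algorithm is needed.
- **10(a)(iii):** reword so that ANOVA and ANCOVA are not called non-parametric.

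The cost is a text amendment, one agreed definition and a little more analysis. The indication date, and whether a visit was patient-initiated, must be recorded. No patients or visits are added. Some risk from differential detection and outcome-related dropout remains.
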